## **A. Objective**

The objective of this project is to leverage the Michigan Surgical Quality Collaborative's (MSQC) existing network and surgeon performance feedback platform to improve opioid prescribing practices for surgeons within the network found to be prescribing in a manner discordant with published guidelines. This work will test how effective this intervention and mechanism are for changing surgeon prescribing behavior and will inform best practices for future surgical quality improvement initiatives.

## **B. Specific Aim/Hypothesis**

To test the effectiveness of a provider-level feedback intervention in optimizing postoperative opioid prescribing. Further, we will assess the acceptability, appropriateness, and adoption of this intervention through survey and qualitative interview mechanisms. We hypothesize that provider-level feedback will allow clinicians to tailor postoperative prescribing more closely to patient consumption and reduce excess postoperative prescribing.

## **C. Background Information*****C1 Project Rationale***

Opioid use in the United States is a national public health crisis, with 130 Americans dying each day from opioid overdose. The state of Michigan has been particularly impacted by the opioid epidemic. In 2017, Michigan ranked number 11 in highest rate of opioid involved deaths in the country. While prescription opioids are routinely used to treat pain following surgery, over-prescription of these same medications increases the risk of new persistent use for the patient and for diversion of excess pills into the community. Decreasing opioid prescribing following surgery presents an opportunity to reduce the amount of risk to the patient and to the community.

Provider-facing feedback interventions - such as the “push reports” utilized in this project - are a promising tool for decreasing post-surgical overprescribing. There is evidence of the success and effectiveness of similar interventions among other aspects of care, such as perioperative antibiotic prophylaxis and electronic health record utilization . Creating tools that integrate opioid prescribing and procedure-specific recommendations could allow clinicians to tailor opioid prescriptions to pain requirements and prevent new opioid dependence.

## ***C2 OPEN and the Michigan Surgical Quality Collaborative***

This project is a collaborative effort between the Opioid Prescribing Engagement Network (Michigan OPEN) and the Michigan Surgical Quality Collaborative (MSQC).

### **OPEN**

The Opioid Prescribing Engagement Network works to steward safe opioid prescribing Michigan by developing evidence-based pain management recommendations for providers, educating patients about safe use and disposal of opioids, and reducing excess opioid pills within the community. OPEN has developed procedure specific prescribing recommendations to curb over-prescribing of postoperative opioids. These recommendations for patients with no preoperative opioid use, were informed by patient-reported data, published studies, and expert opinion. As of February 2020, Michigan OPEN has developed recommendations for 27 procedures for surgical procedures including abdominal, breast, and orthopedic procedures.

### **MSQC**

[figure not shown]
The Michigan Surgical Quality Collaborative (MSQC) is one of the largest surgical collaborative quality improvement programs in the U.S. and captures more than 90% of all general and vascular surgical procedures in Michigan. The MSQC includes surgeons and hospitals statewide that collect and analyze data to improve the quality of care for patients undergoing surgery in Michigan. They are also designated as a Patient Safety Organization designated by the Agency for Healthcare Research and Quality Clinical nurse abstractors (Surgical Clinical Quality Reviewers (SCQRs)) from over 70 hospitals across the state enter procedure and outcomes data – including opioid prescribing information and patient reported outcomes – into the MSQC platform at regular intervals. This data is used for quality improvement and to provide surgeons with regular surgeon specific reports on MSQC's secure web-based platform. These reports contain real-time, risk adjusted, personalized feedback on both surgeon and hospital levels. Providers can also use this platform to easily view their performance in comparison with other de-identified member institutions, drill down into specific cases, and export their own data for further analysis. Each MSQC site also has a surgeon champion who is designated to oversee the implementation and administration of the MSQC program at their institution including supporting the SCQR, promoting and participating in activities directed at improving surgical quality improvement and sharing best practices, and regularly attending the MSQC Quarterly Meetings, Annual Conference, and Surgeon Champion Conference Calls. The role of the MSQC and the Surgeon Champion is not punitive toward individual sites or surgeons.

### ***C3 Project Innovation and Impact***

Currently, MSQC provides a robust platform for quality improvement through tailored and modifiable feedback reports regarding important aspects of perioperative and postoperative care, including complications, mortality, and healthcare utilization. Each quarter, MSQC hospitals receive dashboards regarding benchmarks of surgical care in which hospital performance is displayed against blinded peer data. In this study, we will harness this robust infrastructure to identify surgeons who are outliers in surgical opioid prescribing and deliver specific feedback to them through an email push reporting mechanism.

### **D. Methodology**

*Figure 1 Overview of Study Methodology*

### ***D1 Identification of Surgeon Outliers***

Using existing MSQC data from 1/1/2019 – 2/28/2021, 217 surgeons have been identified as outliers by the MSQC team. Only cases that had valid prescribing data and surgeon National Provider Identifier (NPI) were considered. Prescribing data for the following surgeries were included: Laparoscopic Cholecystectomy, Open Cholecystectomy, Laparoscopic Appendectomy, Open Appendectomy, Minor Hernia, Abdominal Hernia, Laparoscopic Colectomy, Open Colectomy, Vaginal

Hysterectomy, Laparoscopic Hysterectomy, Total Abdominal Hysterectomy, Thyroidectomy, Carotid Endarterectomy, Laparoscopic Anti-Reflux and Hiatal Hernia Surgery, Creation, Re-siting, or Closure of Ileostomy or Colostomy, Open Small Bowel Resection or Enterolysis. These procedures were then grouped into categories based on the number of pills (5 mg oxycodone equivalents) recommended by opioid prescribing guidelines. We will use 2019 guidelines for 2019 data and 2020 guidelines for 2020 and 2021 data

*Table 1: Prescribing Guidelines by Procedure Group*

Procedure category	Procedures
0-5 pills	Thyroidectomy
0-10 pills	Laparoscopic Anti-Reflux and Hiatal Hernia Surgery, Laparoscopic Appendectomy, Open Appendectomy, Minor Hernia, Abdominal Hernia, Laparoscopic Cholecystectomy, Carotid Endarterectomy
0-15 pills	Open Cholecystectomy, Laparoscopic Colectomy, Open Colectomy, Vaginal Hysterectomy, Laparoscopic Hysterectomy, Total Abdominal Hysterectomy, and Creation, Re-siting, or Closure of Ileostomy or Colostomy
0-20 pills	Open Small Bowel Resection or Enterolysis

Median prescribing was calculated using all cases in a specific procedure category at a specific site for which there is a prescribing guideline. If median prescribing of the surgeon was >1 pill (7.5 MME) above current guidelines, they were considered outliers.

## **D2 Site Enrollment and Protections**

Prior to initiation of the research described in this protocol, the study team will contact hospitals with surgeons identified as outliers. Sites that agree to participate in the research by allowing the team to access their identifiable data and send push reports will be required to sign an Exhibit B-1 authorizing the release of the Patient Safety Work Product (PSWP) pursuant to the purpose of Opioid Prescribing Engagement Network Research Activities. This Exhibit B-1 will outline how the site's data will be used in research but will not include information that would bias the study. Exhibit B-1 language will have appropriate approval from legal reviewers at the University of Michigan. The study team will work with the Surgeon Champion and the Surgical Clinical Quality Reviewer at each selected site to identify the appropriate signatory for such a document and to get the document signed and returned to the study team (either through directing the team to the appropriate individual or routing the paperwork to the appropriate individual and returning the paperwork to the study team depending on the preference of the site and the Surgeon Champion/SCQR). The individual administrator who signs the Exhibit B-1 for the site will not be alerted as to which surgeon(s) at their site may be receiving the intervention push report.

For sites who do not complete this paperwork we will look only at de-identified data at the site level to examine prescribing changes. This control arm will not receive the push report intervention.

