### ***D3 Control Arm***

The study team will enroll sites that did not sign the Exhibit B-1 and surgeons at sites who signed the Exhibit B-1 but for whom no contact was available into a control arm. The study team will not have access to identifiable data for sites that did not sign the Exhibit B-w and will obtain and analyze only de-identified site level data.. Those who are moved back to the control arm will be de-identified before re-inclusion in the data file. The study team will use this data to examine prescribing changes.

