### ***D4 Individual Level Push Report Intervention***

All surgeons belonging to sites that signed the Exhibit B-1 document and identified as outliers will be eligible to receive the push-report intervention. The template for provider-level push-report emails has been developed by the study team and informed by surgeon specific reports already available through MSQC and previous quality improvement work led by the OPEN team. During this study, the template will be populated with the individual surgeon data and sent as emailed push reports to surgeons eligible to receive the intervention.

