#### ***D4B Sending the Push Reports***

The push reports will be sent to surgeons at sites who have signed the Exhibit B-1 over the course of four weeks. This will include all surgeons at sites who have signed Exhibit B-1s before the initiation of the push report launch for whom the study team has contact information. Sites who did not sign the Exhibit B-1 and/or surgeons for whom the team was unable to gather updated email addresses for push reporting and/or for whom the email address was no longer valid will be excluded from the intervention arm and moved to the control arm.

The push report will be sent via using a secure email client. The email will be sent to the email the surgeon has provided to MSQC as their official email. In the case of multiple email addresses, the study team will send the email to the most secure account available (e.g. .edu, .gov, .org rather than Yahoo, Gmail, etc).

All surgeons who practice at hospitals and for whom we have a current email address who have signed the Exhibit B-1 will receive a push report email from the study team. Read receipts will be embedded in each push report email to see if surgeons have opened the push report. If they have not, the study team will follow-up with the same email on a weekly basis for a total of 4 weeks or until they open the email, whichever comes first. Emails will be sent to prescribers in this fashion unless they directly contact the study team to request otherwise and/or their hospital/health system revokes permission.

[figure not shown]

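### Surgeons flagged for high past prescribing are compared with site-level control data that no section shown limits to flagged surgeons; D2 and D3 should state that limit

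*Protocol*

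**What the plan says.** D1 applies a flagging rule (surgeon median more than 1 pill, 7.5 MME, above guideline) to data from 1/1/2019 to 2/28/2021 and reports that "217 surgeons have been identified as outliers by the MSQC team". D2 then approaches hospitals that have flagged surgeons.

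The intervention arm is defined in D4: "All surgeons belonging to sites that signed the Exhibit B-1 document and identified as outliers will be eligible to receive the push-report intervention".

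The control arm has two parts. D3 states: "The study team will enroll sites that did not sign the Exhibit B-1 and surgeons at sites who signed the Exhibit B-1", the second group being those without contact details. For non-signing sites, D2 says "For sites who do not complete this paperwork we will look only at de-identified data at the site level to examine prescribing changes", and D3 says the team "will obtain and analyze only de-identified site level data". For the second group, D4B says that surgeons without a usable email address "will be excluded from the intervention arm and moved to the control arm", and D3 adds: "Those who are moved back to the control arm will be de-identified before re-inclusion in the data file".

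E1 defines the primary outcome as average OME after the intervention, adjusted for surgery type. Its only case filter is valid prescribing data and a surgeon NPI.

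On who is sent the report, D4B reads more widely than D4: "All surgeons who practice at hospitals and for whom we have a current email address who have signed the Exhibit B-1" are to receive it, with no mention of outlier status in that sentence.

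**The concern.** One arm is defined by surgeons selected on high past prescribing. The main part of the other is defined by hospitals. D2's outlier condition decides which hospitals are approached, not whose cases within them are counted. If MSQC supplies whole-site figures, the two arms differ by selection before any email is sent.

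The effect depends on the contrast:

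- **Post-intervention average (E1).** Flagged surgeons start higher than a site average that includes their unflagged colleagues. The bias runs against the report.
- **Change in prescribing (the purpose named in D2 and D3).** The only pre-period the protocol names is the flagging window. A group selected on high values in that window will fall afterwards without any intervention, while a whole-site average falls much less. The bias runs in favour of the report.

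This is not simply a matter for an analysis plan. D2 and D3 already fix who the controls are and the level at which their data arrive. If only whole-site aggregates are released, no later model can pick the flagged surgeons out of them.

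**Working it through.** The protocol gives no sample size, effect size, SD or case volume, so it has no figure of its own to reproduce. The check has a textual step and an illustrative numerical step.

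**1. Every limit on whose data are used**

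| Section | Limit stated | Does it restrict non-signing sites' data to flagged surgeons? |
|---|---|---|
| D1 | 217 surgeons flagged | Not stated |
| D2 | Hospitals with flagged surgeons approached; site-level data from non-signers | No; it limits hospitals |
| D3 | Non-signing sites enrolled; site-level data only | No |
| D4 | Reports to flagged surgeons at signing sites | Intervention arm only |
| D4B | Non-signing sites and surgeons without a usable email go to control | No |
| E1 | Valid prescribing data and NPI | No |

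**2. Direction, from the truncated-normal formula (no report effect)**

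Let p be the share of surgeons flagged, SD the spread of observed surgeon averages and r their reliability; all three are assumed. With c = z(1 − p) and λ = φ(c)/p:

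- spurious fall in flagged surgeons = (1 − r) × SD × λ
- remaining gap above the all-surgeon mean = r × SD × λ

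For p = 0.20, SD = 30 OME and r = 0.7: c = 0.842, φ(c) = 0.280, λ = 0.280/0.20 = 1.40, and SD × λ = 42.0.

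- Fall = 0.3 × 42.0 = 12.6 OME.
- Gap = 0.7 × 42.0 = 29.4 OME.

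Over p from 10% to 50%, SD from 15 to 45 OME and r from 0.5 to 0.9, the fall runs from 1.2 to 39.5 OME. That range is wide because SD and r are set freely.

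**3. Size, from a simulation of the D1 rule (no report effect)**

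From the protocol: the Table 1 guideline caps, the 1-pill margin and 7.5 MME per pill. Assumed: mean true excess 0 or −2 pills; between-site SD 0 or 1.5; between-surgeon SD 2 or 4; surgeon-by-category SD 1; case SD 4 or 6; 3 or 8 surgeons per site; one or two procedure categories per surgeon. That gives 64 scenarios per case count. Only sites with at least one flagged surgeon are kept, and half sign at random. Intervention is flagged surgeons at signing sites; control is everyone at non-signing sites.

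False difference in change, intervention minus control, in OME, with the flagging window as baseline:

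| Baseline cases per surgeon | Simple change: range (median) | Baseline-adjusted: range |
|---|---|---|
| 10 | −12.0 to −1.7 (−4.2) | −5.9 to +0.3 |
| 30 | −5.3 to −0.6 (−1.8) | −2.7 to +0.5 |
| 50 | −3.5 to −0.4 (−1.1) | −1.6 to +0.2 |
| 100 | −2.1 to −0.2 (−0.6) | −0.9 to +0.2 |

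Post-intervention average, from the 32 one-category scenarios: flagged surgeons sit about 10 to 40 OME above whole-site controls. At 30 cases the range is +12 to +38 (median +23). More cases per surgeon do not shrink this gap.

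**4. What changes the change-score result**

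- Flagged-only controls: within 0.7 OME of zero.
- Whole sites in both arms: within 0.4.
- A fresh baseline after the flagging window: within 0.5. This helps only a change analysis, not the post-period gap.

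These residuals are simulation noise.

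**5. Mixed control arm**

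If a share w of control cases comes from flagged surgeons without contact details, and they behave like the intervention surgeons, both biases shrink by about (1 − w). At w = 0.5 the post-period gap of 10 to 40 becomes about 5 to 20 OME.

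**The case against.** The strongest reply is that an outlier-only comparison is probably what is meant. D1 fixes a pool of 217 surgeons, D2 approaches only hospitals with flagged surgeons, and D3 speaks of surgeons being re-included in a data file, which suggests one existing file of outliers. The site-level wording may describe how the data are de-identified, not whose cases are in them. Figure 1, the methodology overview, is not available here and could settle it. This stands: the text is silent and does not state a whole-site comparator. A reader might infer that it does, and that goes too far.

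Four further limits also stand.

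- A reader might infer that the main harm is false credit to the push report. On E1's outcome as written the bias has the opposite sign and is much larger. False credit arises only in a change analysis based on the flagging window, which the protocol never calls a baseline. Baseline and model choice may properly sit in an analysis plan.
- A reader might infer that the no-contact surgeons in the control arm are unflagged. D4 limits eligibility to outliers, so surgeons moved out of the intervention arm under D4B are flagged by context. The gap concerns the non-signing sites.
- A reader might infer that flagged-only controls remove all bias. The simulation lets sites sign at random; in the protocol the arms form by site signature and email availability.
- Nearly all numerical inputs are assumed.

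What does not stand is the suggestion that the matter can be left alone. If outlier-only data are intended, a sentence in each section records it. If not, the comparator is unsound and must be changed before the data pull.

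**Conclusion.** The point holds as a gap in the stated comparator that should be fixed. The textual part is firm: no section shown limits non-signing sites' data to flagged surgeons, while the intervention arm is so limited. The consequence is conditional on whole-site data being used. In that case flagged surgeons sit about 10 to 40 OME higher on the primary outcome with no report effect, beyond the protocol's own 7.5 MME flagging margin. A simple change from the flagging window is biased by about −12 to −0.2 OME, depending mainly on cases per surgeon. These figures show direction and rough scale; they do not estimate the bias in this study. Confidence is medium, because an outlier-only pull may already be intended.

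**What to change.** Add to D2 and D3 wording such as: *Control data are limited to surgeons flagged by the D1 rule, at non-signing sites or at signing sites without a valid email address. MSQC applies this limit before de-identified release.* MSQC did the flagging, so it can supply outlier-only means and counts by coded site, procedure category and period, pooling small cells where a site has a single flagged surgeon.

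If release terms do not allow outlier-only data from non-signing sites, compare whole sites with whole sites in both arms, keep no-contact surgeons with their own site, and state the dilution. With flagged surgeons doing 16% to 63% of cases at the kept sites (assumed scenarios), a true fall of 7.5 OME would show as 7.5 × 0.16 = 1.2 to 7.5 × 0.63 = 4.7 OME.

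Either option removes the selection mismatch. Neither removes the bias from allocation by site signature and email availability, which the report should acknowledge.

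Separately, reconcile D4B's wording on who is sent the report with D4's limit to outliers.

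The cost is protocol wording and a different data pull, with no added patients or staff, and some lost precision if small cells are pooled. The protocol does not settle whether an outlier-only cell from a non-signing site counts as site-level data under D3; the fallback is there for that reason.

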### ***D3 Control Arm***

The study team will enroll sites that did not sign the Exhibit B-1 and surgeons at sites who signed the Exhibit B-1 but for whom no contact was available into a control arm. The study team will not have access to identifiable data for sites that did not sign the Exhibit B-w and will obtain and analyze only de-identified site level data.. Those who are moved back to the control arm will be de-identified before re-inclusion in the data file. The study team will use this data to examine prescribing changes.

### ***D4 Individual Level Push Report Intervention***

All surgeons belonging to sites that signed the Exhibit B-1 document and identified as outliers will be eligible to receive the push-report intervention. The template for provider-level push-report emails has been developed by the study team and informed by surgeon specific reports already available through MSQC and previous quality improvement work led by the OPEN team. During this study, the template will be populated with the individual surgeon data and sent as emailed push reports to surgeons eligible to receive the intervention.

#### ***D4A Description of the Push Report***

Surgeons receiving provider-level push report notifications will receive an email displaying their personal prescribing performance compared to OPEN prescribing guidelines and their de-identified peers. Because no case information except opioid prescribing will be included in the push report, the push report will also include a link to the existing, secure MSQC data platform that displays more information about the case so the surgeon can further investigate their prescribing if desired. The email will also contain contact information for the study team so as to help any surgeons troubleshoot, learn more, request to stop receiving reports, etc.

#### ***D4B Sending the Push Reports***

The push reports will be sent to surgeons at sites who have signed the Exhibit B-1 over the course of four weeks. This will include all surgeons at sites who have signed Exhibit B-1s before the initiation of the push report launch for whom the study team has contact information. Sites who did not sign the Exhibit B-1 and/or surgeons for whom the team was unable to gather updated email addresses for push reporting and/or for whom the email address was no longer valid will be excluded from the intervention arm and moved to the control arm.

The push report will be sent via using a secure email client. The email will be sent to the email the surgeon has provided to MSQC as their official email. In the case of multiple email addresses, the study team will send the email to the most secure account available (e.g. .edu, .gov, .org rather than Yahoo, Gmail, etc).

All surgeons who practice at hospitals and for whom we have a current email address who have signed the Exhibit B-1 will receive a push report email from the study team. Read receipts will be embedded in each push report email to see if surgeons have opened the push report. If they have not, the study team will follow-up with the same email on a weekly basis for a total of 4 weeks or until they open the email, whichever comes first. Emails will be sent to prescribers in this fashion unless they directly contact the study team to request otherwise and/or their hospital/health system revokes permission.

[figure not shown]

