## D4C Push Report Data Collection

We will collect prescribing data reported through the existing MSQC mechanism for five months from the date of the first push report. In addition to the standard variables reported to MSQC, the study team will collect data on surgeon interaction with the email push report. We will collect information such as who opens the email, who logs into the MSQC platform after receiving the email, and who directly contacts the study team and why. This information will be used to inform who needs to continue receiving push reports, be used in research analyses, and inform quality improvement opportunities based on this methodology.

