## **E. Statistical Design**

### ***E1 Primary Outcome***

The primary outcome will be the average opioid prescribed (measured in oral morphine equivalents [OMEs] adjusted for the surgery type following the intervention. Only cases with valid prescribing data and surgeon NPI will be included for analysis. Prescribing data will be collected for five months following the first push report.

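### Outlier surgeons at signing sites who cannot be emailed are pooled with the controls, so arm depends partly on reachability and two different untreated groups are mixed

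*Protocol*

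**What the plan says.** Protocol D4 sets eligibility: "All surgeons belonging to sites that signed the Exhibit B-1 document and identified as outliers will be eligible to receive the push-report intervention". D2 describes the sites that do not sign: "For sites who do not complete this paperwork we will look only at de-identified data at the site level to examine prescribing changes", followed by "This control arm will not receive the push report intervention".

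D3 then gives the control arm two sources. One is the non-signing sites, for which the team "will obtain and analyze only de-identified site level data". The other is "surgeons at sites who signed the Exhibit B-1 but for whom no contact was available into a control arm". D3 adds that surgeons moved back to control are de-identified before they re-enter the data file. D4B repeats the rule for surgeons whose updated address could not be obtained and for those "for whom the email address was no longer valid will be excluded from the intervention arm and moved to the control arm".

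Surgeons who are sent the report and never open it are not moved. D4B has the email re-sent to them weekly for up to four weeks, and D5 gives them a separate survey.

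On outcome and follow-up, E1 says "The primary outcome will be the average opioid prescribed" after the intervention, adjusted for surgery type. D4C says "We will collect prescribing data reported through the existing MSQC mechanism for five months from the date of the first push report".

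**The concern.** Site signature as a determinant of arm is imposed on the team, because identifiable data cannot be used without it. Reachability as a second determinant is the team's own choice. Under the rule the intervention arm holds only surgeons with a working address. The control arm holds reachable and unreachable surgeons from non-signing sites, plus the unreachable ones from signing sites. If surgeons without a valid address prescribe differently, for whatever reason, that difference appears between the arms even when the report does nothing.

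The moved surgeons are also a different kind of control. They work at sites that agreed to take part, possibly beside colleagues who received reports. Once they are de-identified and pooled, a later analysis may be unable to separate them from the non-signing sites.

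What is at stake depends on the analysis. E1 words the outcome as a post-intervention average, so a difference in prescribing level between reachable and unreachable surgeons would matter. If change from baseline is analysed, as the references in D2 and D3 to prescribing changes may suggest, only a difference in trend would matter.

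**Working it through.** The protocol states no sample size, effect size, number of unreachable surgeons or split between signing and non-signing sites. There is thus no figure of the plan's own to reproduce. The only count is the 217 outliers in D1. What follows shows how the rule behaves under assumed values.

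**Assumptions.** No intervention effect. Reachable surgeons have mean m and unreachable surgeons m + b, the same in both kinds of site. A share p of outliers is at signing sites. The unreachable share is us at signing sites and un at non-signing sites. Control data cover outliers only, and each surgeon counts equally. Differences are control minus intervention.

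**Three ways to treat the undelivered signing-site surgeons**

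- Moved to control (the plan): b × [(1 − p)un + p·us] / [(1 − p) + p·us]. If us = un = u, this is b × u / [(1 − p) + p·u].
- Kept out of both arms and shown separately: b × un.
- Kept in the intervention arm: b × (un − us).

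The first minus the second is b × p·us(1 − un) / [(1 − p) + p·us]. The multiplier of b is never negative. Under these assumptions, keeping the surgeons out of control is therefore never worse than the planned rule, for any p, us and un.

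**Equal unreachable shares (us = un = u), in multiples of b**

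| p | u | Planned rule | Separate group | Added by the move |
|---|---|---|---|---|
| 25% | 5% | 0.066 | 0.05 | 0.016 |
| 25% | 15% | 0.190 | 0.15 | 0.040 |
| 25% | 30% | 0.364 | 0.30 | 0.064 |
| 50% | 5% | 0.095 | 0.05 | 0.045 |
| 50% | 15% | 0.261 | 0.15 | 0.111 |
| 50% | 30% | 0.462 | 0.30 | 0.162 |
| 75% | 5% | 0.174 | 0.05 | 0.124 |
| 75% | 15% | 0.414 | 0.15 | 0.264 |
| 75% | 30% | 0.632 | 0.30 | 0.332 |

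Example for p = 50%, u = 15%: 0.15 / (0.50 + 0.075) = 0.15 / 0.575 = 0.261. With equal shares, keeping these surgeons in the intervention arm gives 0 throughout.

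At p = 50% the number moved is 217 × 0.5 × u, or about 5, 16 or 33 surgeons for u = 5%, 15% or 30%.

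**Unequal shares, in multiples of b**

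| p | us | un | Planned rule | Separate group | In intervention arm |
|---|---|---|---|---|---|
| 50% | 5% | 30% | 0.175/0.525 = 0.333 | 0.30 | 0.25 |
| 50% | 30% | 5% | 0.175/0.650 = 0.269 | 0.05 | −0.25 |
| 25% | 30% | 5% | 0.1125/0.825 = 0.136 | 0.05 | −0.25 |

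In the last row, keeping the surgeons in the intervention arm leaves a bias about 1.8 times the planned rule's (0.25 / 0.136), with the opposite sign. It also dilutes any real effect to 1 − us of the per-recipient effect: 85% at 15% undelivered, 70% at 30%.

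**The case against.** The strongest reply is that nothing here is randomised, so there is no allocation to protect. Classing surgeons who cannot be sent a report as unexposed is a recognisable choice, and section B does not say whether the aim concerns offering reports or delivering them. This stands as an argument against insisting that these surgeons be analysed in the intervention arm. It does not justify pooling them with non-signing sites, which adds selection and hides a group that could be informative by itself.

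The multiples rest on strong assumptions, and that objection also stands. If the site-level data in D2 and D3 cover all surgeons, the multiples do not apply. If moved surgeons contribute few cases, the effect of the move shrinks. Adjustment for surgery type may absorb part of b. At p = 25% and 50% the move is the smaller part of the total; the rest comes from leaving unreachable surgeons out of the intervention arm.

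A statistical analysis plan could add baseline adjustment or sensitivity analyses. It would not change the allocation rule that D3 and D4B fix, and without a marker the data file may not support such analyses.

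A reader might infer two stronger points. One is that D2 and D4 contradict D3 and D4B. They do not: D4 speaks of eligibility to receive a report, D2 describes the non-signing component, and D3 gives both components of control. The other is that surgeons are reassigned after follow-up has begun. Reports go out over four weeks and follow-up runs from the first report, so this is possible, but the protocol does not say when invalid addresses are identified. It carries no weight here.

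**Conclusion.** The point holds as a design choice worth changing. D3 and D4B make arm depend partly on reachability and pool two different untreated groups. The size and direction of the resulting bias are unknown, because the protocol gives neither b, nor its sign, nor the unreachable shares, nor the split by signature. In the equal-share illustrations the planned rule yields 0.07b to 0.63b, of which 0.02b to 0.33b comes from the move. These figures assume outlier-only control data, equal weight per surgeon and the same b in both kinds of site.

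A reader might conclude that the undelivered surgeons simply belong in the intervention arm. The documents do not support that as a sure improvement. It changes the question to the effect of offering reports and dilutes the effect. It also leaves b × (un − us), which can exceed the planned rule's bias and reverse its sign when signing sites have more unreachable surgeons. The smaller change, a separate marked group, does not dilute the effect and is never worse than the plan under the stated model.

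**What to change.** In D3 and D4B, replace the move to control with wording such as: Outlier surgeons at signing sites with no updated or valid email address receive no report. They carry a marker for signing site, report undelivered, set before de-identification, and are not pooled with the control arm.

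The main comparison is then surgeons at signing sites with a working address, whether or not they opened the report, against non-signing sites. Report the undelivered surgeons by number and baseline prescribing as a separate untreated signing-site group. Repeat the comparison twice as sensitivity analyses: with them in control (the current rule) and with them in the intervention arm (the effect of offering reports).

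The cost is wording in two sections and one marker, plus some loss of control data. At p = 50% with equal shares, the undelivered surgeons would have been 0.025/0.525 = 5%, 0.075/0.575 = 13% or 0.15/0.65 = 23% of control surgeons at 5%, 15% or 30% unreachable. A bias of b times the unreachable share at non-signing sites remains, because those surgeons cannot be identified, and the report should say so. Self-selection by site is not removed.
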